13.1.2 Sensitivity analysis

The following sensitivity analyses for primary efficacy will be performed:

- 1) The primary efficacy analysis as described above will be repeated using the PPS.
- 2) An analysis will be performed by repeating the logistic regression model described in the primary efficacy main analysis, albeit considering the length of the incision/laceration in the logistic regression model instead of the type of wound. This analysis will be performed using the FAS.
- 3) The primary efficacy analysis will be repeated, albeit by considering subjects with missing data for the primary efficacy analysis as experiencing “Yes” dehiscence (i.e., the wound did not remain closed). This analysis will be performed using the FAS. Descriptive statistics of dehiscence assessment following this second imputation rule will be added to the dehiscence descriptive statistics summary described in [Section 13.1.1](#).
- 4) An additional sensitivity analysis will be performed using a Cochran-Mantel-Haenszel (CMH; [Cochran, 1954](#); [Mantel and Haenszel, 1959](#)) test. The dehiscence rates MAR-CUTIS:Dermabond will be analyzed with the CMH test, stratified by skin type (types I to III ; types IV to VI), age group (pediatric with age between 2-21 years; adult with age ≥ 22

years), type of wound (incision; laceration) and treatment (MAR-CUTIS; Dermabond Advanced). This analysis will be performed using the FAS.

- 5) A final sensitivity analysis will be performed by repeating the logistic regression model described in the primary efficacy main analysis, albeit introducing additionally the effect of the center where the subject was treated (given by the center ID) in the logistic regression model. This analysis will be performed using the FAS, and will only be considered if the logistic regression model converges.

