- 2) An analysis will be performed by repeating the logistic regression model described in the primary efficacy main analysis, albeit considering the length of the incision/laceration in the logistic regression model instead of the type of wound. This analysis will be performed using the FAS.
- 3) The primary efficacy analysis will be repeated, albeit by considering all subjects with missing data for the primary efficacy analysis as experiencing “Yes” dehiscence (ie, the wound did not remain closed). This analysis will be performed using the FAS.
- 4) An additional sensitivity analysis will be performed using a Cochran-Mantel-Haenszel (CMH; Cochran, 1954; Mantel and Haenszel, 1959) test. The dehiscence rates MAR-CUTIS:Dermabond will be analyzed with the CMH test, stratified by skin type (types I to III ; types IV to VI), age group (pediatric with age between 2 to 21 years; adult with age  $\geq 22$  years), type of wound (incision; laceration) and treatment (MAR-CUTIS; Dermabond Advanced). This analysis will be performed using the FAS.
- 5) A final sensitivity analysis will be performed by repeating the logistic regression model described in the primary efficacy main analysis, albeit introducing additionally the effect of the center where the subject was treated (given by the center ID) in the logistic regression model. This analysis will be performed using the FAS, and will only be considered if the logistic regression model converges.

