5.2 Sample size

Assuming a dehiscence rates of 3.05% for MAR-CUTIS and 0.85% for Dermabond Advanced, 189 subjects (2:1, 126 MAR-CUTIS vs 63 Dermabond Advanced) ensure a power of 85% to show noninferiority of MAR-CUTIS compared with Dermabond Advanced using a one-sided significance level of $\alpha = 0.05$ and a FM test given a noninferiority margin of 8%.

The assumed dehiscence rates of 3.05% and 0.85% were derived based on the assumption to have 15% of subjects in the trial with lacerations that have a dehiscence rate of 0.5% for MAR-CUTIS and 0% for Dermabond Advanced and 85% of subjects in the trial with incisions, with dehiscence rates of 3.5% for MAR-CUTIS and 1% for Dermabond Advanced.

The assumed noninferiority margin of 8% is based on an average of dehiscence rates observed in previous studies, e.g. [Siddiqui et al. \(2013\)](#); dehiscence between 2%-13%), [Muncie et al. \(2018\)](#); dehiscence rates between 0.8-7.5%) and [Eymann et al. \(2010\)](#); dehiscence rates between 2%-24%). Noninferiority versus a placebo would not be ethical in the context of this trial, and thus has been set conservatively versus an approved IMD (Dermabond).

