13.1.1 Main analysis

The primary efficacy analysis will be performed on the FAS population. All subjects should be treated under equal conditions at all centers and no center-specific variance effects are considered.

During this trial, it is expected that a subject will have only one incision/laceration treated with the IMD (= target wound). In case the subject has more than one incision/laceration, the target wound will be the one with the greatest length (i.e., the longest) that meets the study entry criteria. If the

length of 2 or more wounds is equal, the investigator can choose either of them to be the target wound. Dehiscence will be assessed only for the target wound; for the analysis of the primary efficacy endpoint, only the treated target wound can and will be analyzed.

In the context of the primary endpoint, dehiscence will be defined as “Yes” if the treated wound shows dehiscence until Day 10, or “No” if the wound remains closed. Thus, if the wound is assessed as showing dehiscence at Day 1 but showing no dehiscence at Day 10, dehiscence will be evaluated as “Yes” in the main analysis.

To minimize any possible user bias in the dehiscence rates, investigational centers will provide adequate training to all device users in cooperation with the sponsor. The evaluation of dehiscence, as well as the dehiscence classification and classification according to their grade will be recorded in the e-CRF.

The primary null and alternative hypotheses to be tested in this trial is that treatment with MAR-CUTIS is noninferior to treatment with Dermabond at the margin of 8%, i.e.

$$H_0: p_M - p_D \geq 0.08 \text{ versus } H_1: p_M - p_D < 0.08$$

where p_M is the dehiscence rate of subjects treated with MAR-CUTIS, and p_D is the dehiscence rate of subjects treated with Dermabond. Since the dehiscence rates for both treatments are influenced by several factors, the effect of these will be considered and estimated with a statistical model.

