Based on this contingency table, a comparison of the response rates of both treatments using the method of Farrington-Manning (FM; [Farrington and Manning, 1990](#)) will be performed. The FM estimate for the standard error, the p-value of the FM test regarding non-inferiority, and the two-sided 90% confidence interval (CI) for the difference in dehiscence rates will be obtained and reported.

Non-inferiority of MAR-CUTIS compared with Dermabond Advanced will be declared if the p-value of the FM test is significant at the level $\alpha=0.05$ and the upper limit of the two-sided 90% CI is below the non-inferiority margin of 8%.

Subjects with problems of wound closure are expected to attend the Day 10 visit to see the investigator and assess the wound status. If the subject is unable to attend the Day 10 visit on-site, he/she will be contacted by phone to obtain the information to assess wound closure. For the primary endpoint main analysis on the FAS, any missing data will be imputed as follows:

- Subjects with a provided reason for not attending Day 10 visit related to problems with the wound closure will be counted as failure, i.e. the subject experiences a dehiscence (Dehiscence="Yes")
- Subjects with a dehiscence experienced and recorded before the Day 10 visit (Day 1 or unscheduled visit) will be counted as failure, i.e. the subject experiences a dehiscence (Dehiscence="Yes")
- All other subjects (e.g., lost to follow-up with no dehiscence before) will be counted as a success, i.e. the subject experiences no dehiscence up to Day 10 (Dehiscence="No"), since it is expected that subjects with problems of wound closure would attend the Day 10 visit to see the investigator and assess the wound status, and given the very low expected rate of dehiscence

In any case, all efforts will be made to contact subjects not attending Day 10 visit to gain information about the reason for nonattendance and about potential dehiscence. Descriptive statistics of the evaluation, grading and classification of dehiscence as recorded in the e-CRF and following the imputation rule will be presented for overall and the sub-groups described in Section 8.2.1.

Convergence of model fit

Following [Mallinckrodt et al. \(2008\)](#) we prespecify a fixed sequence of measures to further increase stability of the model to ensure convergence of the primary analysis model. The following prespecified fixed sequence will be applied until a converging model is found:

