1. Fit a logistic regression model to the dehiscence rates using the treatment, age group, and skin type and type of wound as explanatory variables
2. Fit a logistic regression model to the dehiscence rates using the treatment, age group, and type of wound as explanatory variables.
3. Fit a logistic regression model to the dehiscence rates using the treatment and type of wound as explanatory variables.
4. Fit a logistic regression model to the dehiscence rates using treatment as explanatory variable

The first converging model in this sequence will be the primary analysis model. This testing sequence is defined based on the expected clinical relevance of the respective explanatory variables. Moreover, this approach is consistent with the dynamic allocation algorithm implemented for the randomization (see [Section 5.3](#) for more details).

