16.2 List of statistical output documentation

List of outputs:

Total dehiscence rate of target wound assessed until Day 10 (Full Analysis Set)

Total dehiscence rate of target wound assessed until Day 10 - considering wound length (Full Analysis Set)

Total dehiscence rate of target wound assessed until Day 10 - considering imputation of missing values as experiencing Dehiscence (Full Analysis Set)

Total dehiscence rate of target wound assessed until Day 10 - CMH test (Full Analysis Set)

Total dehiscence rate of target wound assessed until Day 10 - considering site effect (Full Analysis Set)

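### Sensitivity analysis 4 lists treatment as a CMH stratum and, once that is corrected, tests for no association instead of the 8% margin, so a non-significant result is not evidence of noninferiority

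*SAP*

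**What the plan says.** SAP 13.1.1 frames the primary hypothesis as whether "treatment with MAR-CUTIS is noninferior to treatment with Dermabond at the margin of 8"%, that is H0: pM − pD ≥ 0.08. Noninferiority needs a significant Farrington-Manning (FM) p-value at 0.05 and also that "the upper limit of the two-sided 90% CI is below the non-inferiority margin of 8"%.

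Five sensitivity analyses follow, worded almost identically in SAP 13.1.2 and Protocol 10.1.3.1.2. Items 1, 2, 3 and 5 rerun the logistic-model analysis with a different analysis set, covariate or imputation rule. Item 4 is different: "The dehiscence rates MAR-CUTIS:Dermabond will be analyzed with the CMH test, stratified by skin type" and then by age group, "type of wound (incision; laceration) and treatment (MAR-CUTIS; Dermabond Advanced). This analysis will be performed using the FAS".

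Neither document gives item 4 a margin, a risk difference, a confidence interval, a significance level or a rule for reading the result. The output list in SAP 16.2 names only "Total dehiscence rate of target wound assessed until Day 10 - CMH test (Full Analysis Set"). SAP 8.1 says that table shells are in a separate document, which was not available.

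**The concern.** There are two separate problems.

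- **Wording.** Treatment is the comparison, so it cannot also define the strata.
- **Hypothesis.** After that correction, CMH asks whether there is any conditional association (common odds ratio 1). With few events it will usually be non-significant whether or not the excess is below 8 points. Placed among sensitivity analyses of a noninferiority endpoint, such a p-value can be taken as reassurance that it does not give.

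What is at stake is a usable robustness check. At the planning rate the Dermabond arm has no event in 0.9915^63 = 58% of trials, and SAP 13.1.1 already provides a fallback for non-convergence. A check that avoids the logistic fit and refers to the margin would therefore be useful.

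**Working it through.** **Inputs.** SAP 5.2: 126 vs 63 subjects, rates 3.05% and 0.85%, margin 8%, one-sided 0.05, power 85%. The rates come from 15% lacerations and 85% incisions: 0.15 × 0.5 + 0.85 × 3.5 = 3.05, and 0.85 × 1 = 0.85. The CMH level is not stated; two-sided 5% and 10% are assumed.

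**Plan's own figure.** The FM score test with restricted maximum-likelihood rates, enumerated exactly over all outcomes, has power 85.8%. The stated 85% is reproduced. Its error rate at 8.85% vs 0.85% is 5.1%.

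**Literal reading.** In a stratum with n1 MAR-CUTIS and n0 Dermabond subjects, m events among N subjects and x MAR-CUTIS events:

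- E = n1·m/N
- V = n1·n0·m·(N − m) / [N²(N − 1)]

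With one arm per stratum, n1 or n0 is 0, so x − E = 0 and V = 0 throughout. The statistic is 0/0.

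**Corrected reading, one stratum, 1/63 Dermabond events.** Worked case 11/126: m = 12, E = 126 × 12/189 = 8, V = 126 × 63 × 12 × 177/(189² × 188) = 2.511, z = 3/1.585 = 1.893, p = 0.058. For FM, the rates restricted to differ by 0.08 are 0.0938 and 0.0138, the standard error is 0.0298, z = (0.0714 − 0.08)/0.0298 = −0.287, and p = 0.387.

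| MAR-CUTIS events | Difference | CMH p | FM p | 90% upper limit | Noninferior? |
|---|---|---|---|---|---|
| 4/126 | 1.6% | 0.52 | 0.009 | 5.6% | yes |
| 8/126 | 4.8% | 0.15 | 0.126 | 9.6% | not shown |
| 11/126 | 7.1% | 0.058 | 0.387 | 12.5% | not shown |

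Six events pass FM (limit 7.7%). Every count from 7 to 11 fails noninferiority with CMH p > 0.05; at a 10% level this holds for 7 to 9 only.

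**Frequencies (exact, unstratified; shares of all trials).**

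| True rates | CMH level | CMH non-significant | Non-significant and FM fails |
|---|---|---|---|
| 3.05% vs 0.85% | 5% | 97.4% | 11.9% |
| 3.05% vs 0.85% | 10% | 88.5% | 3.1% |
| 8.85% vs 0.85% | 5% | 33.6% | 28.5% |
| 8.85% vs 0.85% | 10% | 18.8% | 13.7% |

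If the Dermabond rate is 2.5% or 5% (assumed range), CMH at 5% is non-significant at the margin in 48% or 60% of trials.

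**With strata.** Simulation with 28 lacerations (15%), 40 subjects of skin types IV-VI and 30 aged 2-21, assuming no skin or age effect. The margin scenario sets MAR-CUTIS incisions to 10.3%: 0.15 × 0.5 + 0.85 × 10.3 = 8.83, which is about 8 points above 0.85. CMH at 5% is non-significant in about 97% (planning) and 34% (margin); at 10%, about 86% and 18%. With the roughly 40 lacerations of Protocol 7.2.1, the 5% figures are 97% and 32%.

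**Alternatives at the margin (nominal 5%) and at planning rates.** The stratified score interval wrongly shows noninferiority in about 3.4-4.6% of trials and has power of about 76-82%, across 28 or 40 lacerations, with or without collapsing. The Mantel-Haenszel risk difference with Sato variance errs in about 6.0-7.3%. If the factors are independent, the smallest of the eight strata expects 28 × 40 × 30/189² = 0.9 subjects, so collapsing will be needed in most trials.

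**The case against.** The strongest reply is that nothing in the plan is contradicted. Neither document says that a non-significant CMH result would count as noninferiority, only the FM rule decides, and the listing of treatment corrects itself because the literal version cannot be run. That stands: the wording problem is editorial, and the second problem concerns interpretation and lost value, not a wrong decision rule.

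The plan works at one-sided 0.05, so two-sided 10% is arguably the natural CMH level. The discordance is then smaller (3.1% and 13.7% instead of 11.9% and 28.5%). This is also right, and it narrows the size without removing the point.

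Discordance is not itself harm. At planning rates it reflects missed noninferiority, and at the margin FM has already failed. The trials that could mislead are the 5.1% in which FM wrongly shows noninferiority. In practically all of those CMH is non-significant at either level, so it does not flag them. That is a small but real failure for a robustness check.

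The shells might add an interval. This cannot be excluded, but the method should be fixed in the text in any case.

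The choice of a score interval over Mantel-Haenszel is a matter of method, and the excess error of the latter is modest. Even so, it lies on the unfavourable side in a noninferiority trial.

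**Conclusion.** The concern holds. As written, item 4 is undefined; corrected, it tests a hypothesis that does not involve the margin and cannot support or undermine the noninferiority conclusion in a direct way. A non-significant result is expected in about 97% of trials at planning rates and about a third at a true 8-point excess (two-sided 5%), or about 86-88% and 18-19% at two-sided 10%. A significantly adverse CMH result is only indirect evidence against noninferiority; at the 5% level it coincided with FM noninferiority in under 0.1% of simulated trials.

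These figures assume a CMH level that the plan does not give, and no skin-type or age effect. The trial's decision rule, type I error and sample size are not affected. The change should be made, but it is not critical to the primary result.

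**What to change.** Amend item 4 in SAP 13.1.2 and Protocol 10.1.3.1.2:

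1. Delete treatment from the stratification list, leaving wound type, skin type and age group.
2. Replace or supplement the CMH p-value with the stratified risk difference, MAR-CUTIS minus Dermabond, and a two-sided 90% stratified score (Miettinen-Nurminen) interval whose upper limit is compared with 8%. State the stratum weights. Do not use the plain Mantel-Haenszel interval.
3. Prespecify collapsing: if any stratum lacks an arm, drop skin type, then age group. This follows the order in SAP 13.1.1, of which the SAP says "This testing sequence is defined based on the expected clinical relevance of the respective explanatory variables".
4. If the CMH p-value is kept, give its significance level and say that non-significance is not read as support for noninferiority.
5. Add the interval to the output list in SAP 16.2.

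The cost is wording in two documents and modest programming; no new data are needed. Power for this analysis is about 76-82% at planning rates, against about 86% for the unstratified FM test, which is acceptable for a sensitivity analysis.

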### Study Centers:

Up to 22 study centers located in the European Union

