5.3 Randomization

Subjects (ie, the unique subject identifier [ID] consisting of center ID and subject ID) will be randomly allocated to treatment according to a randomization scheme designed using the covariate-adjusted dynamic allocation method as implemented in Balance ([Medidata, 2015](#)). The algorithm combines complete randomness with a minimization method ([Pocock and Simon, 1975](#)), not only looking at marginal balances, but also considering the treatment balances overall and within individual strata, to ensure a balanced treatment allocation. Based on the expected clinical relevance of the explanatory variables for incision and laceration closure, the algorithm is implemented by assigning a different weight to the stratification factors to be included in the trial and minimize unbalances (i.e., wound type having more importance than the other two factors, and age group having more importance than skin type). Further details regarding the parameters used to implement the randomization in Balance are documented in the form “Balance Study Configuration Requirements”.

The incision/laceration will be prepared for closure as per the standard of care at a treating hospital. The treating physician will assess the need and perform closure of deep tissue layers as necessary before proceeding with the randomization and subsequently with the closure of the last (dermal) layer with the IMD.

Eligible subjects will be randomized 2:1 to MAR-CUTIS or Dermabond Advanced.

The study will include 3 levels of stratification as randomization factors:

- By wound type (lacerations and incisions)
- By skin type according to the Fitzpatrick classification (types I to III vs. types IV to VI)
- By age group (aged 2 to 21 years and ≥ 22 years)

Additionally, center will be considered as a further randomization factor as recommended by ICH E9.

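### Sensitivity analysis 5, the only efficacy analysis that includes center, almost surely has no finite maximum-likelihood fit, and the plan defines neither convergence nor a fallback

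*SAP*

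**What the plan says.** On allocation, SAP 5.3 lists wound type, skin type and age group, and then states: "Additionally, center will be considered as a further randomization factor as recommended by ICH E9". Protocol 7.4.4 agrees, and SAP 7.1 records the addition as a change from the protocol.

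On the main analysis, SAP 13.1.1 starts from the position that subjects are treated alike at all centers and that "no center-specific variance effects are considered". The primary model contains skin type, age group, wound type and treatment. None of the four steps in the convergence sequence has a center term, and the CMH analysis (SAP 13.1.2, item 4) does not stratify by center.

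Item 5 of SAP 13.1.2, and the same item in protocol 10.1.3.1.2, adds center ID to the logistic model on the FAS. It "will only be considered if the logistic regression model converges". Nothing is named to take its place. SAP 16.2 nevertheless lists an output for the site effect.

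The protocol synopsis gives the number of sites as "Up to 22 study centers located in the European Union".

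**The concern.** Adding center ID to a model fitted in proc logistic means one parameter per center; the SAP does not use the term fixed effect, but that is the natural reading. With few events and many centers, most of those parameters cannot be estimated. The plan would then contain a center analysis in name only.

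There are reasons to want a working one. The trial is open-label, and protocol 7.4.7 accepts that the dehiscence assessment may be biased and relies on training given by the sites. Wound preparation and deep closure follow each hospital's standard of care (protocol 7.4.4). These are plausible routes for center-level differences, although no document gives any figure for between-center variation in dehiscence.

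What is at stake is a robustness check, not the primary conclusion: a reader would not learn whether the result holds when subjects are compared within centers.

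**Working it through.** **Inputs.** SAP 5.2: "Assuming a dehiscence rates of 3.05% for MAR-CUTIS and 0.85% for Dermabond Advanced"; 126 and 63 subjects; one-sided 5% level; Farrington-Manning test; margin 8 points; stated power 85%. Synopsis: at most 22 centers. The number and size of enrolling centers are not given, so equal sizes are assumed below.

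**The plan's own figures.**
- Rates: 0.15 × 0.5% + 0.85 × 3.5% = 3.05%, and 0.15 × 0% + 0.85 × 1% = 0.85%. Both reproduce.
- Power: exact binomial enumeration of the Farrington-Manning test at 126/63 gives 85.8%, in line with the stated 85%. (The asymptotic formula gives 79.2%.)

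**Expected events.** 126 × 0.0305 = 3.84; 63 × 0.0085 = 0.54; total 4.38. Exact binomial calculation gives P(at most 4 events) = 55%, P(at most 8) = 97% and P(at least 22) = 6 × 10⁻¹⁰.

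**Does a finite fit exist?** If a center has no event, the likelihood keeps rising as that center's coefficient goes to minus infinity (quasi-complete separation). A finite estimate therefore requires an event in every center. Four events reach at most 4 centers, which leaves at least 18 of 22 without one. With K equal centers, approximately:

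P(every center has an event) = [1 − 0.9695^(126/K) × 0.9915^(63/K)]^K

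For K = 5: 0.9695^25.2 × 0.9915^12.6 = 0.411, and (1 − 0.411)^5 = 0.07. This is an upper bound, because the other covariates can also cause separation.

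| Equal centers | Upper bound on P(finite fit), planning rates |
|---|---|
| 2 | 80% |
| 3 | 46% |
| 4 | 20% |
| 5 | 7% |
| 6 | 2% |
| 10 | 0.0035% |
| 22 | about 5 × 10⁻¹⁷ |

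Unequal center sizes make event-free centers more likely and lower these bounds. Higher event rates do not rescue 22 centers: with the same rate in both arms the bound is 4 × 10⁻⁷ at 8%, 0.04% at 13% and 11% at 24%. The last two rates are the upper ends of two of the literature ranges cited in SAP 5.2.

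**Simulation of the model as written** (treatment, wound, skin, age and center; 800 trials per number of centers). Separation occurred in 97.9% of trials with 2 centers, 99.4% with 5, and 100% with 10 and with 22.

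**What software may do.** An illustrative Newton-Raphson fit to separated data met a relative-gradient tolerance of 10⁻⁸ at iteration 19. The largest coefficient was then about 18 in absolute value and still growing by about 1 per iteration. Failure to converge may therefore not be flagged.

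**Which replacement works?** A center-stratified Mantel-Haenszel risk difference was computable in all 3,000 simulated trials with 22 centers (mean 2.19 points, SD 2.10; crude difference 2.18, SD 1.92). The choice of variance matters:

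| Variance with Mantel-Haenszel weights | Meets 8% margin at a true 8-point excess (8.85% vs 0.85%) | Fails although primary test passes |
|---|---|---|
| Sato | 6.5–7.6% | at most 0.4% |
| Farrington-Manning restricted | 4.0–5.1% | about 2–6% (planning rates) |

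The Sato interval is liberal and almost never disagrees with the primary result. The restricted version holds its level and can disagree. At planning rates without center heterogeneity it passes in about 80–82% of trials, against 84–85% for the primary test in the same simulations.

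**The case against.** The strongest reply is that item 5 is one of five sensitivity analyses, its condition is stated openly, and the non-inferiority rule in SAP 13.1.1 does not use it. Sparse events are also not specific to center: the four-factor primary model without center was separated in about 98% of simulated trials. With about four events, a reader could find the center of each in the subject listings, because the subject identifier contains the center ID. All of this is correct, and it is why the point is minor. It does not repair item 5: the primary model has a prespecified sequence for non-convergence, and item 5 has nothing.

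Three stronger readings are tempting, and the documents do not support them.
- A reader might infer that center was left out of the primary model because item 5 covers it. The SAP makes no such link; its stated ground is equal conditions at all centers.
- A reader might infer that the model cannot converge and so will certainly not be run. The exact statement is that no finite estimate exists. Software may still report convergence, so meaningless output is as real a risk as omission.
- A reader might infer that center is never accounted for. It is used in the allocation, major protocol deviations are shown by center (SAP 10.3), and the protocol presents the product questionnaire by center (10.1.3.2). The gap concerns the efficacy analyses.

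Nor do the documents show that training differs between sites: protocol 7.4.5 provides instruction and a video on both devices to each site.

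**Conclusion.** The point holds, as a minor one. The only efficacy analysis that includes center has at most about a 7% chance of a finite fit with 5 equal centers and essentially none with 10 or more. It will either be dropped or carry uninterpretable center terms, and the SAP does not say which. The primary non-inferiority decision is not affected.

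The conclusion rests on the planning rates, on equal center sizes (which favor the plan), and on reading center ID as a set of fixed terms. It does not depend on reaching the maximum of 22 centers. A usable fit is plausible only with a handful of centers, and even with 2 the full model was separated in 97.9% of simulated trials.

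**What to change.** Replace item 5 with a center-stratified risk difference on the FAS:
- Use Mantel-Haenszel weights n_M × n_D / (n_M + n_D) per center.
- Use a Farrington-Manning/Miettinen-Nurminen restricted (score) variance, not the Sato or Wald variance. State how the restricted rates are obtained. Estimating them from the arm totals over all centers is preferable, since centers average only 189/22 = 8.6 subjects if all 22 enrol, and center-by-center estimates would make the test more conservative.
- Compare the upper limit of the two-sided 90% interval with 8%.
- Prespecify that centers with subjects in only one arm are pooled, for example within country.
- State that separation counts as non-convergence for any logistic fit. This also touches the primary sequence, where even the treatment-only model was separated in about 59% of simulated trials, so the SAP must say what follows if its last step is separated.

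If item 5 is kept, the minimum is that definition of non-convergence plus this analysis as the named fallback.

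The cost is one SAP paragraph, an entry in SAP 7.1, a revised output title in SAP 16.2 and a short program, all before database lock. The downsides are the need for a pooling rule, the loss of the wound, skin and age adjustment in this one analysis, and a pass rate at planning rates a few points below the primary's.
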